### **Activities at Liverpool CDSS**

The overall objective is to define the key immunological events involved in DILI. The project is divided into 2 parts. In Part 1, drug-specific immune responses in subjects with an elevation in liver enzymes and corresponding control subjects will be analyzed. In Part 2 the phenotype and function of drug-responsive T-cells will be characterized. The objectives, main deliverables, and methodological approaches for each part of the study are described in the following sections.

#### **Part 1: Drug-Specific Immune Response**

**Specific objective:** To characterize the drug-specific stimulation of PBMCs from subjects with atacecestat-associated elevation in liver enzymes.

**Deliverables:** (1) Diagnosis of DILI using biological tests; (2) characterization of drug-specific PBMC responses in subjects with atacecestat-associated elevation in liver enzymes and tolerant controls.

**Brief description of work:** PBMC samples from subjects will be analyzed to determine whether study drug stimulates lymphocytes to proliferate and/or secrete cytokines. Methods: To define the role of functional antigen-specific T-cell subsets (T helper [Th]1, Th2, Th17, Th22, CD8+) in DILI, the T-cell stimulatory capacity of the parent drug, metabolites, and structurally-related compounds will be profiled using the lymphocyte transformation test (endpoint [3H] thymidine) and enzyme-linked immunospot (ELISPOT) for monitoring effector T-cell responses. The mitogen phytohemagglutinin and recall antigen tetanus toxoid will be used as positive controls to confirm the proliferative activity of the PBMCs. The negative control will be cell culture medium containing the same quantity of solvent used to dissolve the drug. If the frequency of drug-specific T-cells is too low to detect a T-cell response directly, PBMC from certain subjects will be cultured with drug for up to 4 weeks to generate drug-responsive T-cell clones before analysis of antigen specificity.

## Part 2: Phenotype and Function of Drug-Responsive T-Cells

**Specific objective:** To define the phenotype and function of drug-specific T-cells.

**Deliverables:** (1) Generation and expansion of drug-specific T-cell clones; (2) characterization of the phenotype, function and cross-reactivity with structurally related compounds of T-cell clones; (3) define mechanistic pathways of drug presentation to T-cells.

**Brief description of work:** T-cells will be cloned from subjects and characterized in terms of antigen specificity, phenotype, and function (proliferation, cytolytic activity, cytokine secretion, and tissue homing characteristics). The involvement of the major histocompatibility complex in drug presentation will be assessed using (1) human leukocyte antigen (HLA) blocking antibodies and (2) mismatched or partially HLA-matched antigen presenting cells. Multiplex cytokine analysis and ELISpot will be used to analyze cytokine and effector molecule (eg, perforin, granzyme B, FasL) secretion. The requirement for processing in antigen presentation will be measured by assessing the kinetics of T-cell receptor internalization and through the use of inhibitors of antigen processing. Chemokine receptors expressed on clones will be profiled using flow cytometry.

8.3.	Healthcare Resource Utilization Questionnaire (HRUQ)	50
8.4.	Accommodation and Occupational Status	50
	REFERENCES.....	52
	ATTACHMENTS.....	54
Attachment 1:	Statistical Operational Plan (access to study data and flow of information)	54

Attachment 2:	Sample Size Justification for Biomarker Interim Analyses	65
Attachment 3:	Geriatric Depression Scale (GDS)	67
Attachment 4:	Impact of Events Scale	68
Attachment 5:	Rules for Partial Concomitant Medication Dates	69
Attachment 6:	Potentially Clinically Important Criteria for Laboratory Tests	70

AMENDMENT HISTORY

Version 1.0 of the SAP was amended to modify the planned analyses due to the cessation of screening, randomization, and dosing in the study as 17 May 2018. ‘JNJ-54861911’ is changed throughout to ‘atabecestat’.

ABBREVIATIONS

A β	amyloid beta
A-IADL-Q	Amsterdam instrumental activities of daily living questionnaire
AD	Alzheimer's disease
ADCS-ADL-PI	Alzheimer's Disease Cooperative Study - Activities of Daily Living-Prevention Instrument
ADNI	Alzheimer's Disease Neuroimaging Initiative
AE	adverse event
AIBL	Australian Imaging, Biomarkers and Lifestyle Flagship Study of Aging
ANCOVA	Analysis of Covariance
APOE ϵ 4	apolipoprotein E, ϵ 4 allele
ARH	Autoregressive heterogeneous
ARIA-E	amyloid-related imaging abnormalities – edema or effusion
ATC	Anatomical-Therapeutic-Chemical
BMI	Body mass index
CDR	Clinical Dementia Rating scale
CDR-SB	Clinical Dementia Rating scale – sum of boxes
CFI	Cognitive Function Index
CI	confidence interval
CRF	case report form
CRO	Clinical Research Organization
CS	Homogeneous compound symmetry
CSF	cerebrospinal fluid
CSH	Compound symmetry heterogeneous
C-SSRS	Columbia Suicide Severity Rating Scale
DMC	Data Monitoring Committee
DRV	Driving scenes
ECG	electrocardiogram
eCRF	electronic case report form
EM	Expectation-maximization
EQ-5D-5L	European Quality of Life-5 Dimensions-5 Levels
FCI	Financial Capacity Instrument
FCSRT	Free and Cued Selective Reminding Test
FTP	Future Time Perspective
GCP	Good Clinical Practice
GDS	Geriatric Depression Scale
HRUQ	Healthcare Resource Utilization Questionnaire
HSI	Health Status Index
IA	interim analysis
IES	Impact of Events scale
IRB	Institutional Review Board
ITT	Intent-to-Treat
IWRS	interactive web response system
JRD	Janssen Research and Development
LFT	Liver function tests
LS	Least squares
MAR	Missing at Random
MCMC	Monte Carlo Markov chain
MedDRA	Medical Dictionary for Regulatory Activities
MED-drc	Medication instructions – delayed recall
MED-drg	Medication instructions – delayed recognition
MED-irc	Medication instructions – immediate recall
MHIS	Modified Hachinski Ischaemic Scale
MI	Multiple imputation
MMRM	mixed effect model for repeated measurement
MMSE	Mini Mental State Examination
MRI	magnetic resonance imaging

NAB-DLT	Neuropsychological Assessment Battery–Daily Living Test
NAP-drc	Name, Address, Phone number – delayed recall
NAP-drg	Name, Address, Phone number – delayed recognition
NAP-irc	Name, Address, Phone number – immediate recall
PACC	Preclinical Alzheimer's Cognitive Composite
PCI	Potentially clinically important
PD	pharmacodynamics
PET	positron emission tomography
PK	pharmacokinetics
RBANS	Repeatable Battery for the Assessment of Neuropsychological Status
RDO	Retrieved drop-outs
SAE	serious adverse event
SAP	Statistical Analysis Plan
SC	Sponsor Committee
SD	standard deviation
SF	Semantic Fluency
SF-36	Short Form-36 Scale
SSG	Statistical Support Group
SSR	Sample size re-estimation
STAI	State-Trait Anxiety Inventory
SUVr	standardized uptake value ratio
VAS	Visual analog scale
WAIS-IV	Wechsler Adult Intelligence Scale, version IV
WHO-DD	World Health Organization – Drug Dictionary
WMS	Wechsler Memory Scale

1. INTRODUCTION

This statistical analysis plan (SAP) contains definitions of analysis populations, derived variables and statistical methods for the analysis of efficacy and safety for study 54861911ALZ2003.

Screening, randomization, and dosing in this study was stopped on 17 May 2018. Randomized subjects were to continue in the double-blind treatment phase without treatment (as allowed by protocol) for approximately 3 to 6 months from cessation of dosing. This permitted continued safety monitoring of the subjects per protocol. The planned last-patient-out date is 17 September 2018, except for some subjects who may require further follow-up.

At the time of cessation of screening and randomization, 557 (34%) subjects of the planned 1650 had been randomized. The planned duration of treatment was 54 months. As of the time of cessation of dosing, no subject had more than 27 months of treatment and 447 had 12 months of treatment or less.

As a result of the significantly reduced sample size, the objectives of the study as stated in the protocol and in Section 1.1 below cannot be evaluated. Safety outcomes will be summarized with descriptive statistics. The planned interim analysis of CSF A β ₁₋₄₀ was performed but other planned interim analyses will not be performed. Between-group comparisons of selected efficacy outcomes will be performed. Other efficacy outcomes will be summarized with descriptive statistics

1.1. Trial Objectives

1.1.1. Primary Objective

The primary objective of this study is to determine whether treatment with atabecestat slows cognitive decline compared with placebo treatment, as measured by a composite cognitive measure, Preclinical Alzheimer Cognitive Composite (PACC), in amyloid-positive subjects who are asymptomatic at risk for developing Alzheimer's dementia.

1.1.2. Secondary Objectives

The key secondary objective of this study is the following:

- To determine if atabecestat will slow the decline of cognitive function and performance of everyday activities, compared with placebo, based on the Cognitive Function Index (CFI).

The other secondary objectives of this study are the following:

- To assess the overall safety and tolerability of atabecestat versus placebo.
- To determine if a decline in activities of daily living can be detected based on the ADCS-Activities of Daily Living-Prevention Instrument (ADCS-ADL-PI) scale, and if so, to assess the effect of atabecestat compared with placebo.
- To compare changes in cognitive performance between atabecestat and placebo based on the Repeatable Battery for the Assessment of Neuropsychological Status (RBANS).

- To determine if the Neuropsychological Assessment Battery–Daily Living Tests (NAB-DLTs) for Memory and Attention can detect decline in cognitive function, and if so, to assess the effect of atabecestat compared with placebo.
- To assess the effect of atabecestat compared with placebo on the Clinical Dementia Rating (CDR) scale, including progression from CDR 0 to CDR 0.5 or higher.
- To assess the plasma and cerebrospinal fluid (CSF) pharmacokinetics (PK) of atabecestat following chronic treatment using a population PK approach and to explore their relationship with efficacy and safety parameters (including biomarkers).
- To assess the effects of atabecestat on accumulation of cerebral fibrillar amyloid, as measured by amyloid Positron Emission Tomography (PET) imaging.
- To assess the effects of atabecestat on markers of neurodegeneration (e.g., tau peptides) in CSF compared with placebo.
- To assess the maintenance of atabecestat effects on markers of A β processing in CSF and plasma compared with placebo.

1.1.3. Exploratory Objectives

The exploratory objectives of this study are the following:

- To investigate the effect of atabecestat compared with placebo on brain volume as measured by volumetric Magnetic Resonance Imaging (MRI).
- To investigate the impact of atabecestat compared with placebo on markers of synaptic dysfunction on task-free functional MRI.
- To assess the effects of atabecestat on additional downstream markers of neuronal injury, neurodegeneration, or inflammation in CSF compared with placebo.
- To assess the effects of atabecestat on progression of tau spreading pathology in the brain as measured by tau PET imaging.
- To explore if baseline markers of neurodegeneration (e.g., volumetric MRI, CSF t-tau or p-tau, or tau PET) are related to cognitive decline and response to treatment with atabecestat.
- To explore the correlation between the effect of atabecestat on biomarkers (e.g., amyloid PET, plasma A β , CSF A β and t-tau or p-tau, tau PET) and clinical outcomes.
- To explore the impact of disclosure of amyloid status on questionnaires probing subject perception of amyloid imaging and concern about developing Alzheimer’s disease (AD) dementia.
- To investigate the effect of atabecestat compared with placebo on cognition as measured by a computerized cognitive battery.
- To investigate the effect of atabecestat compared with placebo on function as measured by the Financial Capacity Instrument (FCI).
- To investigate the effect of atabecestat compared with placebo on medical resource utilization as measured by the Healthcare Resource Utilization Questionnaire (HRUQ) scale.

- To investigate the effect of atabecestat compared with placebo on health outcomes as measured by the Short Form-36 (SF-36) and European Quality of Life-5 Dimensions (EQ-5D-5L) scales.
- To explore the ability of the Cognitive Function Index-acute (CFI-a) to measure decline of cognitive function and performance of everyday activities.
- To explore the effect of atabecestat compared with placebo on instrumental activities of daily life (AIDL) as measured by the Amsterdam IADL questionnaire (A-IADL-Q).

1.2. Trial Design

This is a multi-center, double-blind, placebo-controlled, randomized, parallel-group study assessing the efficacy and safety of atabecestat over approximately 4.5 years of treatment in subjects (60 to 85 years of age) who are asymptomatic and at risk for developing Alzheimer's dementia due to evidence of elevated amyloid accumulation based on CSF or amyloid PET imaging.

The study will consist of 3 phases: a screening phase of approximately 90 days during which subject eligibility will be assessed; a fixed dose, double-blind treatment phase during which eligible subjects will receive randomly assigned study drug once daily for up to 4.5 years; and a follow-up phase to be conducted 7 to 28 days after the last dose of study drug. This study will be conducted in an outpatient setting. The maximum study duration for a subject will be 58 months (3-month screening phase + 54-month double-blind treatment phase + 1-month follow-up phase).

Prior to Amendment 3 of the protocol, the fixed dose, double-blind treatment phase included the following treatment groups: placebo, atabecestat 10 mg, and atabecestat 25 mg. Beginning with Amendment 3, the double-blind phase treatment groups are: placebo, atabecestat 5 mg, and atabecestat 25 mg. A total of 11 subjects were randomized prior to the implementation of Amendment 3. Subjects randomized to the atabecestat 10 mg group prior to Amendment 3 and still being dosed after implementation of Amendment 3 will be dispensed atabecestat 5 mg tablets at visits after implementation of Amendment 3. The dosing regimen for all subjects is once-daily, preferably in the morning between 7:00 am and 11:00 am.

1.3. Statistical Hypotheses for Trial Objectives

This section describes the pre-specified statistical hypotheses. However, given the cessation of screening, randomization, and dosing, no formal statistical hypothesis testing will be done.

There are two families of statistical hypotheses: a primary family in which the atabecestat dose groups are compared to the placebo group on the primary efficacy endpoint and a secondary family in which the atabecestat dose groups are compared to the placebo group on the key secondary efficacy endpoint.

The statistical null hypothesis for the primary efficacy endpoint is that there is no difference between either atabecestat dose group and placebo for cognitive decline as measured by the PACC change score at Month 54 (Year 4.5). The alternative hypothesis is that at least one atabecestat dose group is different from placebo for cognitive decline at Month 54 (Year 4.5).

The statistical null hypothesis for the key secondary efficacy endpoint is that there is no difference between either atabecestat dose group and placebo in the decline of cognitive function and performance of everyday activities as measured by the Cognitive Function Index change from baseline at Month 54 (Year 4.5). The alternative hypothesis is that at least one atabecestat dose group is different from placebo in the decline of cognitive function and performance of everyday activities at Month 54.

A gate-keeping strategy combined with a multiple comparison procedure will control overall Type I error over both families of hypotheses at 0.05 (two-sided). Details of the multiple-testing strategy are provided in Section 5.1.1.

1.4. Sample Size Justification

The decline in PACC from baseline was assessed using data from clinically normal populations in the Alzheimer's Disease Neuroimaging Initiative (ADNI); Australian Imaging, Biomarkers, and Lifestyle Flagship Study of Aging (AIBL); and ADCS Prevention Initiative studies. The average difference in PACC decline at 36 months in AIBL between subjects with and without elevated brain amyloid was 1.40 units (95% CI: 0.52 to 2.29), and the standard deviation (SD) at Week 144 (Month 36) was estimated at 2.44 units. If a similar decline in PACC at Month 54 is seen and the SD is 2.44, then 385 completers per treatment arm would provide 83% power (at the 2-sided alpha of 0.05) to detect a difference from placebo of 0.49. The SD at 54 months will likely be higher. If the SD at month 54 increases by 20% to 2.93, then 555 completers per group would be required in order to maintain the same power. The sample size is estimated based on a mixed effects repeated measures (MMRM) model assuming a constant correlation of 0.5⁷. Under the above assumptions and assuming the attrition is no more than 30%, a total of 1,650 randomized subjects (550/treatment arm) will be required at minimum, and 2,400 subjects (800/treatment arm) at maximum. The treatment difference of 0.49 represents 35% of the 1.40-unit difference, or a 35% slowing of decline in PACC in subjects with elevated brain amyloid. If the average time from amyloid positivity to dementia is 15 years¹⁶⁶, then, assuming linear decline, a 35% slowing of cognition may translate into approximately a 5-year delay in the onset of dementia. A 5-year delay could lead to a 57% reduction in the number of patients with dementia¹⁸.

A total of 1,650 randomized subjects (550/treatment arm) will be required, if the attrition does not exceed 30%. This sample size may be further adjusted for increased variability or attrition rate.

1.5. Randomization and Blinding

Randomization

A stratified permuted block randomization will be used in this study. There are 2 stratification factors: country and APOE ε4 carrier status (yes/no). Subjects will be assigned to 1 of 3 treatment groups in a 1:1:1 ratio based on a computer-generated randomization schedule prepared by a CRO under the supervision of the sponsor. The randomization scheme will be implemented in an interactive web response system (IWRS). The IWRS will assign a unique

treatment code for each subject, which will dictate the treatment assignment and matching study drug kit(s) for that subject.

Blinding

Under normal circumstances, the blind should not be broken until all subjects have completed the study and the database is finalized. Otherwise, the blind should be broken only if a specific emergency treatment or course of action would be dictated by knowing the treatment status of the subject. Subjects who have had their treatment assignment unblinded should continue to return for scheduled evaluations.

Data that may potentially unblind the treatment assignment (i.e., study drug concentrations in serum or CSF; treatment allocation, longitudinal CSF/PET biomarker data, or other specific laboratory data) will be handled with special care to ensure that the integrity of the blind is maintained and the potential for bias is minimized. This can include making special provisions, such as segregating the data in question from view by the investigators, clinical team, or others as appropriate until the time of database lock and unblinding.

2. GENERAL ANALYSIS DEFINITIONS

2.1. Subject IDs

In some cases, subjects who screen fail for reasons that are subsequently addressed may be considered for re-screening after approval by the sponsor's medical monitor. In addition, subjects in screening at the time of a previous temporary pause in screening and randomization could be re-screened. In the analysis datasets, data from multiple screening periods for re-screened subjects will be mapped to a single unique subject ID. The data handling rules described below will be applied to all the data collected for that unique subject ID.

2.2. Treatment Group Labels

The following treatment group labels will be used in summary tables:

- Placebo
- Atabecestat 5 mg: This group will include subjects randomized to atabecestat 10 mg prior to Amendment 3.
- Atabecestat 25 mg

2.3. Reference Start Date and Analysis Phases

The analysis reference start date (Study Day 1) is defined as the date of the first dose of study medication. The Study Day of an event start or stop date is defined relative to the analysis reference start date as:

- Event date – analysis reference start date + 1, if the visit/event date is on or after the analysis reference start date, or

- Event date – analysis reference start date -1, if the visit/event date is before the analysis reference start date

Study Days <1 will be considered in the Screening analysis phase; Study Days \geq 1 (there is no Study Day 0) will be considered in the Double-blind analysis phase.

For visit dates prior to, or on, the date of the last dose of study medication, an Analysis Day will be defined as above relative to the analysis reference start date. For visit dates after the treatment end date, an Analysis Day is defined relative to the treatment end date as: Visit date – treatment end date + 1.

- Analysis reference start date (date of first dose as above) for all timepoints after first dose (whether before or after last dose)
- For assessments after last dose, use last observation before last dose as the reference time point.

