2.4. Visit Windows

As subjects do not always adhere to the protocol visit schedule, the following rules are applied to assign actual visits to analysis visits. Listed below are the visit windows and the target days for each visit. The same definitions will apply to visits before or after the treatment end date using the Analysis Day as defined in Section 2.3 above. The time period description will be appended with '(On-Trt)' for post-baseline visits on or prior to the treatment end date. The time period description will be appended with '(Off-Trt)' for post-baseline visits after the treatment end date. If a subject has 2 or more actual visits in one visit window, the visit closest to the target day will be used as the protocol visit for that visit window. The other additional visit(s) will not be used in the summaries or analyses but they can be used for determination of clinically important endpoints. If 2 actual visits are equidistant from the target day within a visit window, the later visit will be used.

All assignments will be made in chronological order. Once a visit date is assigned to a visit window, it will no longer be used for a later time point except for the endpoint. Listed below (Table 1) are the visit windows and the target days for each visit defined in the protocol.

Table 1: Visit Windows for on and off-treatment Analysis

Scheduled Visit Number	Time period (label on output)	Time Interval (Day*)	Target Time Point (Day)
7	Baseline	-120 to 1	1
8	Week 2	2 to 22	15
9	Week 4	23 to 36	29
10	Week 6	37 to 50	43
11	Week 8	51 to 64	57
12	Week 10	65 to 81	71
13	Month 3	82 to 106	92
14	Month 4	107 to 134	120
15	Month 5	135 to 165	148
16	Month 6	166 to 211	183
17	Month 8	212 to 256	239
18	Month 9	257 to 288	274
19	Month 10	289 to 333	302
20	Month 12	334 to 410	365
21	Month 15	411 to 501	456
22	Month 18	502 to 592	547
23	Month 21	593 to 683	638
24	Month 24	684 to 774	729
25	Month 27	775 to 865	820
26	Month 30	866 to 956	911
27	Month 33	957 to 1047	1002
28	Month 36	1048 to 1138	1093
29	Month 39	1139 to 1229	1184
30	Month 42	1230 to 1320	1275
31	Month 45	1321 to 1411	1366
32	Month 48	1412 to 1502	1457
33	Month 51	1503 to 1593	1548
34	Month 54	1594 to 1684	1639
	Month >54	1685 to ∞	1685

* Relative to analysis reference start date if visit date is prior to or on the treatment end date. Relative to treatment end date if visit date is after treatment end date.

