‘End point (On-Trt)’ is defined as the last available post-baseline result among the on-treatment visits. Unscheduled visit results are included in this definition and will be considered as the endpoint value if the unscheduled visit result is the last post-baseline result available among all on-treatment visits. ‘Baseline (Off-Trt)’ will be defined as the same as ‘End point (On-Trt)’. ‘End point (Off-Trt)’ is defined similarly to ‘End point (On-Trt)’ but based on off-treatment visits.

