5.3. Key Secondary Endpoint

5.3.1. Definition

The key secondary efficacy endpoint is the change from baseline in the subject-reported Cognitive Function Index (CFI) total score. The CFI is a modified version of the Mail-in Cognitive Function Screening Instrument²⁰, a subject- and informant-reported outcome measure developed by the ADCS. The subject-reported and informant-reported CFIs are assessed on the same schedule: 5 to 10 days before randomization, then annually after randomization through Month 48, and at Month 54 (or early termination if not performed at previous visit). This assessment includes 14 questions that assess the subject's perceived ability to perform high-level functional tasks in daily life and sense of overall cognitive functional ability (yes=1; no/does not apply=0; maybe=0.5 for each question) and 1 additional question about whether the subject has seen a doctor in the last year about memory concerns. Study subjects and their informants independently rate the subject's abilities.

The CFI total score is the sum of the first 14 questions, with higher scores indicating greater impairment (range = 0 to 14). If there are fewer than 5 (<30%) missing items, an imputed total score will be calculated as a prorated total based on the observed items:

$$14 * \left(\frac{\text{Total score of non-missing items}}{\text{Total number of non-missing items}} \right)$$

Imputed total scores will be rounded to 1 decimal place. If there are 5 or more missing items, the total score will be missing. A subject-reported and an informant-reported total score will be calculated. Change from baseline in the CFI total score will be calculated at each time point. For off-treatment visits, change from the off-treatment baseline (see Section 2.4) will also be calculated.

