- An increase in Suicidal Ideation Score from baseline at any post-baseline, time point in the // on-treatment period (treatment-emergent suicidal ideation compared to baseline).
- An increase in Suicidal Ideation Score from <4 at baseline to ≥ 4 at any post-baseline, time point in the on-treatment period (treatment-emergent serious suicidal ideation compared to baseline).
- An increase in Suicidal Ideation Score from 0 at baseline to ≥ 4 at any post-baseline, time point in the on-treatment period (emergence of serious suicidal ideation compared to baseline).

In these summaries, the denominator is the number of subjects meeting the baseline criterion.

Listings including additional C-SSRS details will be created for subjects with any suicidal ideation or behavior.

The above summaries will be presented for off-treatment time points, using the off-treatment baseline as the reference time point.

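### SAP 2.3 gives two time origins for off-treatment visits: its first closing bullet counts from first dose, while its own Analysis Day rule and Table 1 count from treatment end

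*SAP*

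**What the plan says.** **Time origin.** SAP 2.3 defines Study Day from the date of first dose. It defines a separate Analysis Day, which for visits on or before last dose uses the same origin. After that the origin changes: "For visit dates after the treatment end date, an Analysis Day is defined relative to the treatment end date as" visit date minus treatment end date plus 1. SAP 2.4 builds the visit windows on this count: "The same definitions will apply to visits before or after the treatment end date using the Analysis Day as defined in Section 2.3 above". The Table 1 footnote repeats it: "Relative to treatment end date if visit date is after treatment end date".

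Two bullets close SAP 2.3, directly after the Analysis Day rule. The first names the analysis reference start date, that is first dose, "for all timepoints after first dose (whether before or after last dose".

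**Baseline.** The second bullet reads: "For assessments after last dose, use last observation before last dose as the reference time point". SAP 2.4 sets Baseline (Off-Trt) equal to End point (On-Trt), which "is defined as the last available post-baseline result among the on-treatment visits". Unscheduled results count, and a visit on the treatment end date is on-treatment.

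**The concern.** A programmer deriving off-treatment visit labels meets two instructions in one section. If the first bullet is applied to Analysis Day, the label no longer shows time since withdrawal. It shows time since first dose, which differs from subject to subject by the length of treatment. An off-treatment table by time point would then put subjects at different intervals after stopping in one row, and spread subjects at the same interval over many rows. The study was stopped for hepatic enzyme elevations, and SAP 6.1 and 6.1.1 repeat the laboratory and liver summaries off treatment, so those tables should have one unambiguous clock.

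The second bullet raises a smaller question: whether the reference value for off-treatment change is always the one that SAP 2.4 defines.

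**Working it through.** The plan gives no figure to reproduce. The check assigns the same visit to Table 1 under each rule.

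**Formulas.** Let the last dose fall on Study Day D and the visit t days later.
- From treatment end (2.3 body text, 2.4, Table 1 footnote): day = t + 1.
- From first dose (first bullet): day = D + t.
- Difference: (D + t) − (t + 1) = D − 1, almost the whole treatment duration.

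**A visit 90 days after last dose (t = 90).** From treatment end this is Day 91, Month 3 (window 82 to 106), whatever D is. From first dose (D values are illustrative):

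| Last dose on Day | Day from first dose | Table 1 window | Label |
|---|---|---|---|
| 90 | 90 + 90 = 180 | 166 to 211 | Month 6 |
| 180 | 180 + 90 = 270 | 257 to 288 | Month 9 |
| 365 | 365 + 90 = 455 | 411 to 501 | Month 15 |
| 730 | 730 + 90 = 820 | 775 to 865 | Month 27 |

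**All visits from 1 to 183 days after last dose.** With last dose on Day 90, 180 or 365, none of the 183 possible days falls in the same window under both rules. With last dose on Day 28, 24 of 183 agree.

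**Spread of labels at study closure.** Inputs from the SAP Introduction: dosing stopped on 17 May 2018, follow-up of about 3 to 6 months, planned last patient out on 17 September 2018, and no subject above 27 months of treatment. Assume a subject dosed until 17 May whose final visit falls between 17 August (92 days) and 17 September (123 days).
- From treatment end: 92 + 1 = Day 93 (Month 3) to 123 + 1 = Day 124 (Month 4), so 2 labels.
- From first dose: the shortest case is 1 + 92 = Day 93 (Month 3). The longest takes 27 × 30.44 ≈ 822 days of dosing, so 822 + 123 = Day 945 (Month 30, window 866 to 956). Table 1 has 14 labels from Month 3 to Month 30.

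**Baseline rules side by side.** SAP 6.4.2 presents its off-treatment summaries "using the off-treatment baseline as the reference time point", so the second bullet's reference time point is naturally read as the off-treatment baseline and not as a day-count origin. On that reading it picks the same observation as SAP 2.4 except at two edges:
1. With no post-baseline on-treatment result, the bullet admits a pre-dose value; SAP 2.4 gives no off-treatment baseline.
2. A result on the day of last dose is on-treatment under SAP 2.4, but is not before last dose if dates are compared. An ECG is one example: Protocol 9.9.3 records it 1 to 4 hours after dosing, so on the final dosing day it follows the last dose.

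**The case against.** The strongest reply is that the first bullet is a fragment without a verb, that it names the date SAP 2.3 introduces as Study Day 1, and that it may concern Study Day only. The operative windowing text is clear and twice specifies treatment end. This stands as evidence of intent. It does not remove the conflict: the bullet follows the Analysis Day rule, expressly covers time points after last dose, and does not mention Study Day.

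A second reply is that the label counts describe hypothetical subjects and that some off-treatment outputs do not use visit labels. This also stands. End point (Off-Trt) is the last available off-treatment result, and the liver criteria in SAP 6.1.1 count any occurrence after the off-treatment baseline. The counts show how far labels can move, not how many subjects move.

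A reader might also infer that the second bullet sets up a rival baseline throughout. The documents do not support that. It expresses the same idea as SAP 2.4, and the analysis sections point to 2.4, for example SAP 5.3.1: "For off-treatment visits, change from the off-treatment baseline (see Section 2.4) will also be calculated".

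A reader might further infer that the contradiction leaves many subjects without an off-treatment baseline on scales first repeated at Month 12, such as the CFI and CDR. Any such gap comes from the SAP 2.4 definition itself and would remain after SAP 2.3 is corrected. Its size cannot be read from the SAP Introduction, which reports treatment duration and not completed assessments.

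**Conclusion.** The point holds on the time origin: the first closing bullet, applied to Analysis Day, is incompatible with the rule just before it, with SAP 2.4 and with the Table 1 footnote. On the baseline it holds only at the two edges shown. The intended rule appears to be treatment end for the day count and Baseline (Off-Trt) for the reference value, so the bullets are what should change.

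The plan is wrong as written, and the error is minor. If the first bullet were followed, a label could move from Month 3 to as late as Month 27 in the 90-day examples, and closure visits could spread over up to 14 labels in place of 2. These sizes rest on the illustrative dosing durations, on dosing until 17 May 2018 and on 30.44 days per month. The number of subjects at the two baseline edges is not given.

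The reach is limited to off-treatment by-time-point tables, including laboratory and liver summaries, and to the off-treatment baseline at the edges. The latter also decides who enters the off-treatment liver counts, which require values in the normal range at that baseline. SAP 5 restricts off-treatment efficacy to descriptive statistics. It would be wrong to infer that any on-treatment comparison is affected, since those visits are counted from first dose under either rule.

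**What to change.** Make two edits in SAP 2.3:
1. Delete the first closing bullet, or limit it to: *Study Day only; Analysis Day after treatment end is as defined above.*
2. Replace the second closing bullet with: *For assessments after last dose, the reference value is Baseline (Off-Trt) as defined in Section 2.4, which includes results on the treatment end date.*

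SAP 2.4 and Table 1 stay as they are. The cost is two sentences of text, with no new data, no new table and no change to any on-treatment output. Programs already written to Table 1 need only a check that off-treatment days are counted from treatment end and that no pre-dose value serves as an off-treatment baseline.
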